DSMB	Data Safety Monitoring Board	
DSUR	Development Safety Update Report	
EC	Ethics Committee	
EU	European Union	
ECG	Electrocardiogram	
ЕоТ	End of Trial	
FPFV	First Patient First Visit	
GCP	Good Clinical Practice (latest version of ICH E6)	
GDPR	EU General Data Protection Regulation 2016/679	
IB	Investigator's Brochure	
ICF	Informed Consent Form	
ICH	International Council on Harmonisation	
IMP	Investigational Medicinal Product	
ISF	Investigator Site File	
JCI	Joint Commission International	
LPLV	Last Patient Last Visit	
MAH	Marketing Authorisation Holder	
MP	Monitoring Plan	
PI	Principal Investigator (Participating Site)	
PRO	Patient Reported Outcome	
SAE	Serious Adverse Event	
SAP	Statistical Analysis Plan	
SAR	Serious Adverse Reaction	
SOP	Standard Operating Procedure	

SmPC	Summary of Product Characteristics
SUSAR	Suspected Unexpected Serious Adverse Reaction
TMF	Trial Master File
ЗННВ	R-3-hydroxybutyl-R-3-hydroxybutanoate
EN	Enteral nutrition

FUNDING AND SUPPORT

Funder

European Research Council (ERC)

Flemish Government Methusalem Program

TDeltaS

Type of Financial or Non-Financial Support

Non-commercial financial support by research grant AdvG 2017-785809 Non-commercial financial support by research grant METH14/06 Free delivery of the investigational product

ROLES AND RESPONSIBILITIES

The Principal Investigator (PI) is responsible for the conduct of the Trial at his/her Participating Site, and for protecting the rights, safety and well-being of the Trial participants. As such the PI must ensure adequate supervision of the Trial conduct at the Participating Site. If any tasks are delegated, the PI will maintain a log of appropriately qualified persons to whom he/she has delegated specified Trial-related duties. The PI will ensure that adequate training is provided and documented for all Trial staff, prior to conducting assigned Trial-related activities.

It is the Coordinating Investigator's (CI's) responsibility to supervise the general conduct (e.g. Trial progress, communication, protocol training and support of the participating sites, annual reporting to the Ethics Committee (EC), end of Trial notification(s) and results reporting...) of the Trial. The CI fulfils both Investigator and Sponsor responsibilities, as outlined in International Council on Harmonisation – Good Clinical Practice (ICH-GCP) E6(R2) and applicable regulations.

PI and CI shall each be referred to as «Investigator(s)».

TRIAL SYNOPSIS

Title of clinical Trial («Trial»)	A single-centre, placebo-controlled, cross-over randomized controlled trial evaluating the metabolic effects of a ketone ester food supplement in intensive care patients: The KETOCARE RCT		
Protocol Short Title Acronym	The KETOCARE RCT		
Sponsor name	University Hospitals Leuven (UZ Leuven)		
Coordinating Investigator	[name]. [name]		
Contact Address Cl	[name]		
Contact Email Cl	[contact]		
Contact Phone CI	[name]		
Public database nbr	ISRCTN: 13903536		
Sub Investigators	[name]. [name] (UZ Leuven) [name]. [name] (KU Leuven) [name]. [name] (UZ Leuven)		
Medical condition or disease under investigation	Adult critical illness		
Trial rationale	To study the feasibility, safety and tolerability of enteral ketone ester supplementation to increase circulating ketone levels in adult critically ill patients.		
Primary objective	To identify a supplementation dose of enteral ketone esters that is able to increase circulating 3-hydroxybutyrate concentrations in adult crtitically ill patients by at least 0.22 mmol/l.		
Secondary objective(s)	To demonstrate that supplementation of enteral ketone esters is safe.		
Trial Design	Single-center, placebo-controlled, cross-over randomized controlled trial		
	- An increase in plasma 3-hydroxybutyrate by at least 0.22 mmol/l following administration of enteral 3HHB (E)		
	- Plasma levels of 3HHB and metabolites 3-hydroxybutyrate and 1,3- butanediol over time during (6 hour period) and after the intervention (18 hour period) (E)		
Endpoints	- Urine levels of 3HHB and metabolites 3-hydroxybutyrate and 1,3- butanediol over time during (6 hour period) and after the intervention (18 hour period) (E)		
(Efficacy = E;	- Blood glucose concentrations during the 48h-study period (E)		
Safety – S, Tolerability – T)	- Incidence of ketoacidosis during the intervention window and until 18h after stopping study infusion (S		
	- Intolerance for the supplement (including abdominal discomfort or vomiting) (S/T)		
	- Incidence of severe (<40 mg/dl) hypoglycemia during the intervention window and until 18h after stopping study infusion (3HHB or placebo) (S)		
Sample Size	16 patients for each study dose completing the 48h study period (maximum of 48 patients completing the 48h study period in total)		

Dietary supplement, dosage and route of administration	Enteral administration of a ketone ester supplement (3-HHB) in increasing dosage (25g, 50g, 75g)		
Active comparator product	Enteral administration of 5% of glucose		
Maximum duration of treatment and Follow Up of a Participant	Duration of intervention: 48 hours. Clinical follow-up until 48 hours after the intervention or until ICU discharge, whatever comes first.		
Maximum duration of entire Trial	2 years		
Date anticipated First Patient First Visit (FPFV)	I-9-2023		
Date anticipated Last Patient Last Visit (LPLV)	I-9-2025		

I Background, Rationale and Risk Assessment

The majority of prolonged critically ill patients develop muscle weakness and wasting during their stay at the intensive care unit (ICU), which hampers recovery and is associated with longer-term morbidity and mortality [1, 2]. Although preventive measures such as aggressive sepsis treatment and early mobilization have shown some benefit, other effective therapeutic or preventive interventions are currently lacking. Providing parenteral nutrition to supplement insufficient enteral nutrition was found unable to prevent this debilitating condition, whereas in contrast, accepting a macronutrient deficit early during critical illness has shown to accelerate recovery and reduce muscle weakness [3, 4]. In pediatric ICU patients, accepting such an early macronutrient deficit increased plasma concentrations of the ketone body 3-hydroxybutyrate, a direct effect that statistically mediated an important part of the outcome benefits [5, 6]. In adult ICU patients, an early macronutrient restriction did also increase plasma concentrations of 3-hydroxybutyrate, but to a much smaller extent than in pediatric patients and without independently mediating the outcome benefit [6]. One could speculate that the lower impact of withholding early parenteral nutrition on ketogenesis may explain the lower effect size of the intervention in adult patients.

Preclinical research by our group further strengthens the **potential clinical benefit of increasing plasma 3-hydroxybutyrate in critically ill patients**. Indeed, in a mouse model of sepsis-induced prolonged critical illness, we demonstrated that exogenous administration of the ketone body 3-hydroxybutyrate, administered as daily bolus injections of a racemic mixture of R,S-3-hydroxybutyrate sodium salt (3HB-Na), significantly attenuated the development of muscle weakness [7]. Subsequent dose-response and toxicity studies revealed that ketone esters are preferred to ketone salts, with a broader therapeutic window [8]. Indeed, the effective dose of 5g/kg/day of the ketone salt 3HB-Na was close to the toxic threshold [9], whereby increased morbidity and mortality by increased doses are likely explained by excessive sodium intake, since ketone esters have a substantially higher threshold for toxicity.

A potentially **safer alternative** for ketone salts is the ketone ester R-3-hydroxybutyl-R-3hydroxybutanoate (**3HHB**) which is endogenously converted to two 3-hydroxybutyrate molecules [10]. The ketone ester is hydrolyzed to 3-hydroxybutyrate and 1,3-butanediol by esterases that are located in the circulation, in the gastro-intestinal tract, the liver, and other tissues [11]. The butanediol molecule is further metabolized to 3-hydroxybutyrate in the liver by alcohol and aldehyde dehydrogenases [11, 12]. We demonstrated that treatment of septic mice with the ketone ester 3HHB **improved muscle weakness** from a dose of 3.5 g/kg/day onward [13]. Up to a dose of 7 g/kg/day 3HHB, signs of organ damage or liver toxicity were absent. However, septic mice showed a higher peak plasma concentration and slower 3-hydroxybutyrate clearance than healthy control mice, leading to toxicity with a bolus of 14 g/kg/day. **This toxicity of a single bolus was completely avoided by a continuous intravenous infusion of this dose** (i.e. 14 g/kg/day) over 24h, while the protective effect on muscle weakness remained equally present [13]. This preclinical research has led to a patent application PCT/EP2017/081394 which is currently in its national phase.

Mechanistically, we could demonstrate that the muscle protection of 3-hydroxybutyrate treatment was limited to a direct effect on muscle force, whereas the ongoing sepsis-induced muscle atrophy was not affected [7]. The ketone body protection did not appear to be related to its use as an energy substrate, but rather by its effects as a signaling molecule affecting regeneration pathways [7] and by its conversion to cholesterol [14].

The next step in this research is investigating whether ketone esters might prevent or improve debilitating ICU-acquired weakness also in critically ill patients. A first step is to define a well-tolerated and effective dose able to increase the blood 3-hydroxybutyrate in critically ill patients. Oral administration of ketone esters has been extensively tested and found to be safe in healthy adults to induce ketosis, tested for up to 28 days [10, 11, 15].

2 Trial Objectives and Design

2.1 Trial objectives

We were able to demonstrate that treatment of septic mice with the ketone ester 3HHB improved muscle weakness. In order to study this effect in a randomized clinical trial in critically ill patients, we first want to determine a dose of 3HHB that effectively and safely increases plasma 3-hydroxybutyrate concentrations in adult critically ill patients.

To this purpose, we want to test fixed doses of 25 g, 50 g and 75 g of 3HHB in order to reach an increase of 0.22 mmol/l plasma 3-hydroxybutyrate, as was observed with the effective dose of 3HHB in earlier mice studies [13]. The fixed doses of 25 g, 50 g and 75 g that will be tested are based on the human equivalent (0.6 g/kg/day) of the effective and non-toxic dose in rodents (7 g/kg/day) [16]. Sustained ketosis through oral ingestion of the ketone ester 3HHB has previously been shown to be safe in healthy adults, tested at doses between 0.140 and 2.142 g/kg/day for up to 28 days [10, 11, 15].

2.2 Primary Endpoints

The primary efficacy endpoint will be an increase in plasma 3-hydroxybutyrate by at least 0.22 mmol/l following administration of enteral 3HHB.

2.3 Secondary Endpoints

- Plasma levels of 3HHB and metabolites 3-hydroxybutyrate and 1,3-butanediol over time during (6 hour period) and after the intervention (12 hour period)
- Urine levels of 3HHB and metabolites 3-hydroxybutyrate and 1,3-butanediol over time during (6 hour period) and after the intervention (12 hour period)
- Plasma levels of cholesterol (HDL, LDL, total), triglycerides en free fatty acids over time during (6 hour period) and after the intervention (12 hour period)
- Blood glucose concentrations during the 48h-study period
- Incidence of severe (<40 mg/dl) hypoglycemia during the intervention window and until 12h after stopping study infusion (3HHB or placebo)
- Incidence of ketoacidosis during the intervention window and until 12h after stopping study infusion
- Intolerance for the supplement (including abdominal discomfort or vomiting)

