2.4 Trial Design

This will be a single center trial, in adult critically ill patients. With a cross-over design (Fig. 1), patients will receive in random order on 2 consecutive days 3HHB and placebo.

Patients will receive the investigational product between ICU day 4 and 14, to avoid the time of increase in endogenous ketogenesis that we have previously documented to be present in the first 2 to 3 days in ICU [6]. The investigational product (3HHB) or placebo will be delivered through the enteral feeding tube.

Figure 1: Cross-over design of the trial. In group 1, participants will receive 3HHB on intervention day 1, followed by a placebo on intervention day 2. Group 2 will receive placebo on intervention day 1 and 3HHB on intervention day 2. Repetitive blood sampling is indicated in red.

Patients are typically started on enteral nutrition (EN) within 48 hours of admission, unless they are able to eat. EN is delivered for 2x10h per day (8am-6pm and 8pm-6am), with 2x2h interruption (6-8am and 6-8pm) to measure gastric residual volume (Fig 2). EN is usually started at a low rate, and increased depending on tolerance (as deducted in part from gastric residual volumes). For this trial, the caloric intake will be kept constant over the 2 intervention days avoiding the influence of caloric intake on outcome measures. Patients with nasogastric tubes who are not receiving enteral nutrition are also eligible for inclusion. This will allow to study ketone absorption and clearance in both fed and unfed state in the critically ill patient.

Figure 2: 10 hour feeding scheme. Intermittent administration of 3HHB/placebo (in green) every hour for 6 times.

We will administer 3HHB or placebo via repeated small boluses through the nasogastric feeding tube, as is also done for enterally administered medication. The nasogastric tube will be flushed with a 5% glucose solution prior and after administration of 3HBB or placebo to ensure that the bolus has completely entered the stomach while also avoiding clotting of the nasogastric tube.

The first bolus wil be given at 10 am (after 2 hours of enteral feeding) and this wil be repeated 5 times with one hour interval (6 doses in total). After the last bolus, the patient will be fed for three more hours. The next day, this procedure will be repeated (Fig. 1).

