2.5 Translational research

Blood glucose and 3-hydroxybutyrate concentrations will be quantified repeatedly using blood gas analysis and point-of-care devices during the 48h trial window.

For this trial, we will collect blood samples at 10 ± 1 am on ICU test day I, before administration of the first bolus, repeat this every hour, up to I hour after the last bolus (4 pm), and then every 2 hours until 12h post final bolus (4 am on ICU test day 2). We will repeat this on test day 2. In total, 26 samples (104 ml blood) will be collected from each patient. To minimize blood waste and reduce infection, we will use a VAMP system for blood sampling. Each sample consists of I EDTA tube (purple K2E tube - BD Vactutainer 368861) containing 4 ml of blood. Samples will be stored on ice immediately and processed for further analysis. After processing, samples will be frozen at -20°C and stored at -80°C.

We will collect a urine sample from the 24h urine collection at 8 am ± 1 hours at the end of both intervention days. These samples will be processed, frozen and stored at -80°C for further analysis.

As a standard of care, whole blood glucose measurements are performed every 4 hours on arterial blood using a blood gas analyzer in the ICU. Using the left-over of this clinically collected sample, we will also measure 3-hydroxybutyrate using ketone test strips (Nova StatStrip).

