2.6 Expected Duration of the Trial

Patients will receive 3HHB or placebo, which will be administered over 6 hours on two consecutive days in ICU (between ICU day 4 and day 14). Repeated measurements will be done on blood and urine during the 48h intervention. The last sample will be taken on the morning following the 2nd intervention day in the ICU. This is the end of the intervention for the individual patient. We will do a clinical follow-up for at least 48 hours after the intervention.

Since we will only include patients who have an expected ICU stay of at least 5 days, we estimate that we will need a 2-4 month screening period. This can be doubled or tripled when we need to test higher doses of ketones.

3 Trial Population / Eligibility Criteria

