- Urine 3HHB + metabolites values (3-hydroxybutyrate and 1,3-butanediol) measured in collected urine samples

- Parenteral nutrition (kilocalories, amino acids, lipids and carbohydrates cumulatively administered during ICU day 3-4-5-6)

- Enteral nutrition (kilocalories, amino acids, lipids and carbohydrates cumulatively administered during during ICU day 3-4-5-6)

- Biochemical, metabolic, endocrine and inflammatory markers associated with ketone metabolism in blood and urine samples

- Adverse reactions

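### The urine endpoint is worded as a time course during and after dosing, but one sample of the 24 h urine pool per study day supports only a comparison of the 3HHB day with the placebo day

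*Protocol*

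**What the plan says.** The urine endpoint in Protocol section 2.3 reads "Urine levels of 3HHB and metabolites 3-hydroxybutyrate and 1,3-butanediol over time during (6 hour period) and after the intervention (12 hour period"). The synopsis words it the same way but with a longer second window: "over time during (6 hour period) and after the intervention (18 hour period) (E").

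Section 2.5 gives the urine sampling in one sentence: "We will collect a urine sample from the 24h urine collection at 8 am ± 1 hours at the end of both intervention days". The start of the 24 h collection is not stated. Section 2.6 adds "Repeated measurements will be done on blood and urine during the 48h intervention" but gives no further urine times. The data list in section 8.2 has "Urine 3HHB + metabolites values (3-hydroxybutyrate and 1,3-butanediol) measured in collected urine samples". It names neither a urine volume nor collection times.

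On dosing, section 2.4 says "The first bolus wil be given at 10 am (after 2 hours of enteral feeding) and this wil be repeated 5 times with one hour" spacing, so there are six boluses. For blood, section 2.5 says "repeat this every hour, up to I hour after the last bolus (4 pm"), followed by two-hourly samples to 4 am.

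**The concern.** The urine endpoint uses the same time-course wording as the plasma endpoint. Plasma has a dense sampling schedule to support it, and urine has one pooled sample per day. A pool mixes everything voided over its collection period, so the dosing and post-dosing periods cannot be separated afterwards.

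Two things follow. First, the endpoint as defined and the data as collected do not match, so whoever reports it will have to replace it with something else after the fact. Section 2.4 has the primary and secondary endpoints assessed after the first cohort, so the mismatch would surface early. Second, what can be reported is a concentration in pooled urine. That reflects urine output as well as ketone excretion, and the paired comparison sets two days of an ICU patient against each other. Section 3.2 does not exclude renal failure or renal replacement therapy, so patients with altered urine output may be enrolled.

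**Working it through.** **1. The protocol's own sampling count (blood).** Inputs are from section 2.5.
- Hourly, 10 am to 4 pm: 7 samples per day.
- Two-hourly, 6 pm to 4 am: 6 samples per day.
- Total: (7 + 6) × 2 days = 26 samples, and 26 × 4 ml = 104 ml.

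Both figures match the protocol, so the schedule has been read as intended. Plasma has 13 time points per day, enough for a time course.

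**2. The same count for urine.**
- Available: 1 pooled sample per day × 2 days = 2 values per patient.
- Needed for the endpoint as worded: at least 2 periods (during, after) × 2 days = 4 separately collected fractions per patient.

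Neither section 2.6 nor section 8.2 adds a timed fraction. Two daily pools already satisfy the reference in section 2.6 to repeated urine measurements.

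**3. What the pool would cover.** This step assumes a collection from 8 am to 8 am. The range moves both ends by the ± 1 h tolerance and keeps the length at 24 h. The first bolus is at 10 am, and the 6 h dosing period runs to 4 pm.

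| Part of the pool | 8 am to 8 am | Range |
|---|---|---|
| Before the first bolus | 10 − 8 = 2 h | 1 to 3 h |
| Dosing period | 6 h | 6 h |
| After dosing (4 pm to 8 am) | 24 − 2 − 6 = 16 h | 15 to 17 h |

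Compared with the stated post-dosing windows:
- Section 2.3 (12 h): the pool runs 16 − 12 = 4 h too long (range 3 to 5 h).
- Synopsis (18 h): the pool falls 18 − 16 = 2 h short (range 1 to 3 h).

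Under this assumption the pool matches neither window exactly. It would match the synopsis total of 6 + 18 = 24 h only if collection began at the first bolus, and section 2.5 does not say that it does.

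**4. Concentration and amount.** Let A be the amount excreted, V the volume collected and C = A / V the pooled concentration. Comparing the 3HHB day (K) with the placebo day (P):

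C_K / C_P = (A_K / A_P) × (V_P / V_K)

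The ratio of concentrations equals the ratio of amounts only when the two volumes are equal. This is an identity. The documents give no urine outputs or day-to-day variation, so the effect in this trial cannot be sized from them.

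**The case against.** The strongest reply is that the urine data are usable as they stand. A 24 h pool gives one level per study day, and a 3HHB-versus-placebo comparison within patient fits the crossover. The two windows in the synopsis add to 24 h, the length of one collection, so the wording may have been meant cumulatively. This stands in part: the day-to-day comparison is available and only the split is lost. The cumulative reading does not rescue the wording, because both versions of the endpoint name two separate periods within a day and refer to levels over time.

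The pre-dose overlap rests on an assumed 8 am start and would apply alike to both study days. Both points are right, so the overlap is given above only as an assumption with a range.

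On volume, it can be said that a concentration is a level, that no excretion endpoint is contradicted, and that urine output may be captured under renal function in section 8.2 or in routine ICU records. How a secondary variable is normalised may also be left to the SAP, which is not shown. These points limit the volume argument to a recommendation: volume may be available, but the protocol does not tie it to this endpoint. They do not touch the main point, because no SAP can create timed fractions that were never collected.

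A reader might infer that the urine endpoint cannot be reported at all, or that differing urine output will seriously distort it. The documents support neither reading. The pools allow a paired comparison, and nothing in the protocol shows how much urine output varies between the two days.

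**Conclusion.** The point holds as an internal mismatch between the endpoint definition (section 2.3 and synopsis) and the urine sampling (section 2.5). There are 2 urine values per patient where the wording needs at least 4, so levels during and after dosing cannot be told apart. A comparison of the 24 h pool between the 3HHB and placebo days remains possible.

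The count depends only on the stated schedule. The statement that the pool matches neither window depends on the assumed 8 am to 8 am collection. The dependence of concentration on volume is certain in principle but of unknown size here.

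The consequence is confined to one secondary endpoint. The primary endpoint, the sample size and the escalation rule in section 7.1 do not use urine data. The 12 h versus 18 h difference between section 2.3 and the synopsis is a separate inconsistency, which also affects other endpoints and needs its own reconciliation.

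**What to change.** In section 2.3 and the synopsis, redefine the urine endpoint as the amount of 3HHB, 3-hydroxybutyrate and 1,3-butanediol excreted in the 24 h collection (concentration × volume) on each study day, compared within patient between the 3HHB day and the placebo day. In section 8.2, add the 24 h urine volume and the start and stop times of each collection.

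The cost is a change of wording and a few recorded fields from a collection already made, with no extra urine samples or patients. The during/after split is given up, but the current sampling cannot provide it anyway.

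If the sponsor does want the split, the alternative is to specify in section 2.5 separately collected urine fractions for the dosing and post-dosing periods on each day. That means at least 4 fractions per patient instead of 2 samples, with the added collection and assay work. Under either option, the synopsis and sections 2.3, 2.5 and 8.2 should agree.
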